### 8.2.3 Vital Signs

Individual vital sign measurements (seated SBP/DBP, heart rate and oral temperature) will be listed by measurement time and summarized using descriptive statistics as appropriate (i.e., mean, median, range, and standard deviation). Individual change from baseline (screening) in vital sign measurements will be calculated and summarized descriptively. A clinically significant change from baseline will be recorded as a TEAE if deemed appropriate by the Investigator.

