
Statistical Methods
	
Descriptive statistics (mean, standard deviation, median, minimum, and maximum values) will be tabulated for the study population. Subject disposition, demographic and Baseline characteristics, extent of exposure and study termination/withdrawal information will be presented. Descriptive statistics will be presented for each of the

	
evaluable safety and efficacy parameters for change from Baseline as well as value at each time point. Adverse event information will be summarized by age group and narratives were used in presentation of the data for safety monitoring. Serious adverse events (SAEs) will be summarized similarly and narratives presented. Clinical laboratory values will be summarized by time point, subject, and age group. Values and changes from baseline at each time point will be tabulated.

--	------------------------------------------------------------------------------------------------------------------------------------------------------------------------------------------------------------------------------------------------------------------------------------------------------------------------------------------------------------------------------------------------------------------------------------------------------------------------------------------------------

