Subjects will then undergo a Treatment Phase consisting of a treatment period of 12 weeks that will start at Visit 3 (Week 0) and outpatient visits at Weeks 1, 2, 4, 8, and 12 (final visit). At each visit, concomitant medication will be reviewed, weight will be measured, and sufficient quantity of medication will be dispensed to last until the next nominal clinic visit. Medication compliance check will be performed, self-monitored fasting morning blood glucose (finger-stick) will be recorded 3 days weekly in the morning and subjects' diaries will be reviewed. Vital signs (SBP/DBP, heart rate and oral temperature) will be recorded. Adverse events will be monitored and recorded. ORMD-0801 morning treatment will be administered in clinic during Visits 3, 6 and 7.

At Visit 3, urine pregnancy test will be performed for females of childbearing potential. At Visit 8, subjects will have HbA1c evaluations and MRI-PDFF performed. At Visits 3 and 8, a complete physical exam and CAP-Fibroscan will be performed.

At Visits 3 (baseline), 6, 7, and 8, patients will have clinical laboratory evaluations (serum chemistry, hematology) and blood lipids performed. Fasting blood glucose, insulin (also used for HOMA estimates) and adiponectin levels will be measured.

The End-of-Study (EOS) Visit (Visit 9) will be conducted 4 weeks following the last scheduled treatment visit. Subjects concomitant medications will be reviewed, and weight will be measured. A complete physical exam and ECG will be performed and vital signs (SBP/DBP, heart rate and oral temperature) will be measured if deemed necessary by the investigator. Clinical laboratory evaluations [serum chemistry (including liver function tests (LFTs) and blood lipids) and hematology] will be performed. Fasting blood glucose, fasting insulin, HbA1c and adiponectin levels will be measured. Subject diaries will be collected and reviewed for self-monitored fasting morning blood glucose. Adverse events will be monitored and recorded. Subjects who are discontinued early from the study will complete the EOS evaluations at the time of early discontinuation.

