### **3.5 End-of-Study (EOS) Phase (Visit 9, Week 16, Days 112±4)/Early Termination**

The EOS Visit (Visit 9) will be conducted 4 weeks following the last scheduled treatment Visit. Subjects will report to the clinic in the morning following a 10-hour fast. The following procedures will be performed:

- Review of concomitant medication;
- Complete PE, only if the investigator deems it necessary;
- Measurement of weight;
- Collection of unused ORMD-0801 medication;
- 12-Lead ECG, only if the investigator deems it necessary;
- Measurement of vital signs (SBP/DBP, heart rate and oral temperature), only if the investigator deems it necessary;
- Fasted blood samples will be collected for clinical laboratory evaluations (see [Section 6.5.5.1](#) for a complete list of tests performed):
  - Serum Chemistry including liver function tests (LFTs) and blood lipids;
  - Hematology;
- Measurement of fasting blood glucose and fasting insulin for HOMA estimates;
- Review/Collect subject diaries for self-monitored fasting morning blood glucose;
- HbA1c;
- Adiponectin test;
- AEs/SAEs assessment.

Patients who are discontinued early from the study will complete the EOS evaluations at the time of early discontinuation.

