## Table 1 Footnotes

-  Prior and concomitant medications will be reviewed at Screening. Concomitant medications will be reviewed through Visits 2-9.
-  Only if investigator deems necessary.
-  Height measurement and BMI calculation will be performed at Screening only. Weight will be measured as indicated.
-  Serum pregnancy test will be performed at Screening (Visit 1). Urine pregnancy test will be performed at Visit 2 and Visit 3.
-  Blood samples taken prior to dosing in clinic and snack provided after 30-45 minutes at Visit 2, 3, 6, and 7.
-  Study medication will be dispensed and collected at Visits 2-8 and collected at End-of-Study/Early Termination Visit.
-  Vital signs (blood pressure, heart rate, oral temperature). Vital signs will be measured in the sitting position after at least 5 minutes of rest.
-  Serum Chemistry: Sodium, Potassium, Glucose, BUN, Creatinine, BUN/Creatinine, Chloride, Calcium, Protein, Albumin, Globulin (total), A/G Ratio, SGOT (AST), SGPT (ALT), Bilirubin (total), Alkaline Phosphatase, CO2, Creatine Phosphokinase (CPK), Total cholesterol, LDL, HDL, Triglycerides, Thyroid Stimulating Hormone (TSH, screening only). Hematology: Hemoglobin, Hematocrit, RBC, WBC (total count and differential count), Platelets Count, Mean Platelet Volume (MPV), MCV, MCH, MCHC, RDW, Neutrophils (absolute value and %), Bands (ABS CNT), Bands, Lymphocytes (absolute value and %), Monocytes (absolute value and %), Eosinophils (absolute value and %), Basophils (absolute value and %), RBC Morphology. Urinalysis is not performed in this study.
-  Fasting blood glucose and insulin will be used to determine Homeostasis Model Assessment (HOMA) estimates. During an Unscheduled Visit only fasting blood glucose will be collected, if investigator deems necessary.
-  Self-monitoring (finger-stick) of fasting blood glucose will be required 3 days weekly in the morning, before breakfast, and recorded in patient diaries.
-  HCV-Ab (hepatitis C virus antibody), HBsAg (surface antigen of the hepatitis B virus), HBcore-total (total hepatitis B core antibody), HBs Ab (hepatitis B surface antibody), anti-HIV Ab (human immunodeficiency virus antibody).

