### 8.2.7 Handling of Missing, Unused, or Spurious Data

Descriptive statistics and listings will be provided for all data. No substitution of missing data will be used in any calculations. Data points that appear to be spurious will be investigated and

will not be excluded from the listings. Influential cases will be handled in an appropriate statistical manner.

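### Vital signs at Visit 9 (Week 16 or early termination) are taken only at the investigator's discretion, yet the plan summarizes them by time point with no exception, so the Week 16 mean and change may be biased

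*Combined protocol and SAP*

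**What the plan says.** Section 8.2.3 (Vital Signs) states that individual measurements "will be listed by measurement time and summarized using descriptive statistics as appropriate", and that "Individual change from baseline (screening) in vital sign measurements will be calculated and summarized descriptively". It names no visit to be left out. The synopsis, under Statistical Methods, plans descriptive statistics for the "evaluable safety and efficacy parameters for change from Baseline as well as value at each time point".

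The schedule treats Visit 9 differently from the other visits. Table 1 requires vital signs at Visits 1 to 8. For Visit 9, Section 3.5 lists "Measurement of vital signs (SBP/DBP, heart rate and oral temperature), only if the investigator deems it necessary". Section 3.1 says the same: "vital signs (SBP/DBP, heart rate and oral temperature) will be measured if deemed necessary by the investigator". The Visit 9 cell in Table 1 carries footnote 2: "Only if investigator deems necessary". None of these places says what makes a measurement necessary.

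On timing, Section 3.5 says "The EOS Visit (Visit 9) will be conducted 4 weeks following the last scheduled treatment Visit", and it applies the same list of assessments to subjects who stop early, at the time they stop. Section 8.2.7 adds, for safety data: "No substitution of missing data will be used in any calculations".

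**The concern.** If vital signs are taken only where the investigator sees a need, being measured can depend on what the measurement is likely to show. With no substitution for missing values, a Visit 9 mean, median or change from screening describes only those subjects. It would stand in the same table as values from Visits 3 to 8, where every attendee is measured, and a reader would naturally take the step from Week 12 to Week 16 as a change over time. Part or all of that step could come from the change in who was measured.

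Vital signs are a named safety assessment, and safety is the primary endpoint. For subjects who complete treatment, Visit 9 is the only scheduled visit off drug. A second problem is that the same discretionary list serves early termination. A Visit 9 column could therefore mix true Week 16 readings with readings taken at discontinuation, and some subjects who stop early may have no exit reading at all.

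**Working it through.** There is no stated figure to reproduce: the plan gives no SD for any vital sign, no expected share measured at Visit 9, and no power calculation (Section 8.1 says the study is not powered). The check has two parts.

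**Schedule against analysis text**

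| Item | Visits 3 to 8 | Visit 9 / early termination |
|---|---|---|
| Vital signs taken (3.1, 3.4, 3.5, Table 1) | All attendees | At the investigator's discretion |
| Weight and fasted blood samples at Visit 9 (3.5) | – | All attendees |
| Included in value and change summaries (8.2.3, synopsis) | Yes | Not excepted |
| Missing values (8.2.7) | Observed only | Observed only |

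Section 8.2.2 names Visit 8 as the post-dose point for the laboratory shift tables. Section 8.2.3 sets no corresponding limit for vital signs. Followed as written, the schedule and the summary rule can produce a Week 16 row based on a selected subset.

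**Illustration of size**

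Let p be the share measured, ρ the correlation between the reason for measuring and the change in the vital sign, and SD the standard deviation of that change. If the true mean change is 0 and selection favours the upper end of a normal distribution, the expected observed-case mean is

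false mean change = ρ × SD × φ(z₁₋ₚ) / p

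where φ is the standard normal density and z₁₋ₚ the cut-off above which subjects are measured. All three inputs are assumptions.

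For p = 1/3 the cut-off is 0.4307 and φ(0.4307)/0.3333 = 1.091. With SD = 12 mmHg for systolic pressure:

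- ρ = 0: 0 × 12 × 1.091 = 0 mmHg
- ρ = 0.2: 0.2 × 12 × 1.091 = 2.6 mmHg
- ρ = 0.5: 0.5 × 12 × 1.091 = 6.5 mmHg

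The same formula in SD units for other shares measured:

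| Share measured | ρ = 0 | ρ = 0.2 | ρ = 0.4 | ρ = 0.6 |
|---|---|---|---|---|
| 10% | 0 | 0.35 | 0.70 | 1.05 |
| 25% | 0 | 0.25 | 0.51 | 0.76 |
| 50% | 0 | 0.16 | 0.32 | 0.48 |
| 75% | 0 | 0.08 | 0.17 | 0.25 |
| 100% | 0 | 0 | 0 | 0 |

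The mildest non-zero entry, 0.08 SD, is about 1 mmHg at SD 12 (0.08 × 12 = 0.96).

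The numbers behind such a mean would be small. About 30 completers at 2:1 are 20 and 10, so one third measured is about 7 active (20/3 = 6.7) and 3 placebo (10/3 = 3.3).

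**The case against.** The strongest reply is that the documents do not say how investigators will use their discretion. They may measure everyone, since each attendee is already weighed and bled, and the bias is then zero. Selection need not favour high systolic pressure either. Dizziness, fever or palpitations could prompt a reading, so the error could be negative, close to zero for blood pressure, or fall on another sign. This stands. It is why the conclusion is that the summary may be biased, and why the figures are illustrations.

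The wording of Section 8.2.3 also leaves room. Read strictly, the phrase about measurement time attaches to the listing, and summaries are made as appropriate. Section 8 defers further detail to a statistical analysis plan. That latitude is real, but it is not a rule for a discretionary visit. The synopsis asks for values and changes at each time point, and the supplied text contains no exception.

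Three stronger readings are tempting and are not supported:

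- A reader might infer a false difference between arms. The trial is double-blind, so the choice to measure cannot rest on knowing the arm. With the same share measured and the same correlation in both arms, the expected error is equal in each and the expected difference is 0.
- A reader might take perfect selection (ρ = 1) as the headline size. The decision to measure comes before the reading is known, so that case is not realistic.
- A reader might infer that the primary safety evaluation is compromised. Vital signs are required through Visit 8, adverse events and laboratory tests remain mandatory at Visit 9, and no objective asks whether a vital-sign change reverses off drug.

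The discretionary schedule is also stated consistently in three places, so it is a deliberate choice. The fault is that the analysis text was not adapted to it.

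**Conclusion.** The point holds in limited form. The schedule and the summary rule, applied together, allow a Week 16 mean and change from screening that rest on subjects chosen for perceived need, with early-termination readings possibly mixed in. Such a row may be biased and is not comparable with the full-sample rows at Visits 3 to 8. On-treatment summaries are untouched, no planned test is affected, and no between-arm bias is shown.

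Neither the size nor the direction can be derived from the documents. If one third are measured, the SD is 12 mmHg and selection leans toward high systolic pressure, the false mean change runs from 0 (correlation 0) through about 2.6 mmHg (0.2) to about 6.5 mmHg (0.5). The importance is low, but a misleading row is possible and cheap to prevent.

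**What to change.** Preferred: in Sections 3.1 and 3.5 and in Table 1, take seated vital signs in every subject who attends Visit 9 or an early-termination visit, and report early-termination values separately from Week 16 values. This removes the selection by investigator choice and gives early leavers who attend an exit reading. The cost is a few minutes at a visit where each subject is already weighed and has blood drawn, plus a wording change in three places.

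If that is not adopted: add a sentence to Section 8.2.3 stating that discretionary Visit 9 vital signs are listed only, with the number measured per arm, and are left out of the by-time and change-from-baseline summaries. The cost is one sentence; the downside is that there will be no Week 16 vital-sign row.

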### 8.2.4 12-lead ECG

Individual 12-lead ECG assessments will be listed by visit and summarized using descriptive statistics as appropriate (i.e., mean, median, range, and standard deviation for continuous data and frequency for categorical data).

### 8.2.5 Physical Examination

Individual physical examination findings will be listed by visit. A clinically significant change from baseline (Screening) will be recorded as an AE if deemed appropriate by the Investigator.

### 8.2.6 Prior and Concomitant Medications and Supplements

Medications and supplements will be coded using the most current version of the WHO Drug Reference List, which employs the Anatomical Therapeutic Chemical classification system.

All medications and supplements (other than IMP) taken by the subject from Visit 2 through Visit 8 will be considered “concomitant” medications and supplements. Medications and supplements taken prior to Visit 2 that are no longer being taken at the time of Visit 2 will be considered “prior” medications and supplements.

Concomitant medications and supplements will be listed for individual subjects. A similar listing will be prepared for prior medications and supplements taken within 30 days prior to the first dose of IMP. The incidence of these prior and concomitant medications and supplements will be summarized.

### 8.2.7 Handling of Missing, Unused, or Spurious Data

Descriptive statistics and listings will be provided for all data. No substitution of missing data will be used in any calculations. Data points that appear to be spurious will be investigated and

will not be excluded from the listings. Influential cases will be handled in an appropriate statistical manner.

### **8.3 Efficacy Evaluation**

#### **8.3.1 Liver Fat Content**

The analysis of liver fat content will be an Analysis of Covariance (ANCOVA) with treatment, country and site as effects and baseline value as a covariate.

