## 5.2 Randomization

This is a double-blind, randomized, placebo-controlled study. Adult male and female subjects with NASH and type 2 DM will be competitively enrolled at all study sites. Approximately 36 subjects will be randomized in a 2:1 ratio to either ORMD-0801 8 mg BID or to matching placebo.

Integrium, LLC will generate and implement the randomization procedures for this trial. A computer-generated randomization schedule will be used for assigning the treatment groups. The Investigational Site pharmacist will follow this randomization schedule to dispense the appropriate study treatment.

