### 6.4 Efficacy Assessments

Fat content in the liver will be assessed by measuring the final and baseline differences in the MRI-PDFF results. Images generated from the MRI-PDFF scans will be submitted for central reading.

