## 8 STATISTICAL METHODS

This section describes the statistical methods to be used for the analysis and reporting of data collected under Protocol No. ORA-D-N02. Additional details will be provided in the statistical analysis plan.

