### 8.1 Sample Size

Up to 36 patients with NASH and Type 2 DM will be randomized to complete approximately 30 in this multi-center exploratory study. Subjects will be enrolled at 2 sites in Israel and 3 sites in the USA.

The treatment regimen will consist of a soft gelatin capsule containing 8 mg insulin, and 75 mg SBTI. Patients will take one capsule in the morning and one capsule at night, daily, or matching placebo, based on their randomized schedule.

The size of the study population was determined by reviewing the literature for pilot studies and was found to be sufficient to show trends of reducing liver fat content by MRI-PDFF images and CAP-Fibroscan. This study is not powered for statistical significance.

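### Does naming both country and site in the liver-fat ANCOVA, when each site lies in one country, harm the efficacy analysis?

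*Combined protocol and SAP*

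**What the plan says.** Section 8.3.1 gives the one model stated for liver fat: an "Analysis of Covariance (ANCOVA) with treatment, country and site as effects and baseline value as a covariate". It does not say whether site is nested or random, or how sites and countries would be weighted in an adjusted arm mean. It does not mention adjusted arm means or a test of country.

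Section 8.1 gives the geography: "Subjects will be enrolled at 2 sites in Israel and 3 sites in the USA". It also gives the size: "Up to 36 patients with NASH and Type 2 DM will be randomized to complete approximately 30 in this multi-center exploratory study". The same section says the study is not powered for a significance test.

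Section 5.2 sets 2:1 allocation, says patients "will be competitively enrolled at all study sites", and states that "A computer-generated randomization schedule will be used for assigning the treatment groups". It names no stratification factor. Section 6.4 adds: "Images generated from the MRI-PDFF scans will be submitted for central reading".

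Section 8 opens by saying that "Additional details will be provided in the statistical analysis plan"; the combined document has no further text on this model. The Synopsis, under Statistical Methods, promises descriptive statistics by time point and for change from baseline. Those summaries involve no model weights.

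**The concern.** Each of the five sites belongs to exactly one country, so the two country indicators are sums of site indicators. A model with both sets has more columns than it can estimate. Three consequences seem to follow.

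- Country has no degrees of freedom left once site is fitted, so its adjusted effect cannot be estimated or tested.
- Adjusted arm means depend on how sites and countries are weighted, and one natural-looking choice (countries equal and sites equal at once) is not estimable.
- Five site effects in about 30 completers may cost precision, the more so if allocation is not balanced within site.

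At stake would be the single model offered for the MRI-PDFF endpoint: two analysts could publish different arm means from the same data, or one could get a non-estimable result.

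**Working it through.** The plan gives no power, effect size or SD for this endpoint, so there is no stated figure to reproduce. The check is linear algebra, illustrated on simulated data.

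**Inputs.** Two countries and five sites, 2 + 3 (Section 8.1); about 30 completers (Section 8.1); 2:1 allocation (Section 5.2); effects as listed in Section 8.3.1. Assumed: fixed, uniquely coded sites and no interaction with treatment.

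**1. Rank.** Full indicator coding has 1 intercept + 2 arms + 2 countries + 5 sites + 1 baseline = 11 columns. There are four dependencies: the arms sum to the intercept, the sites sum to the intercept, Israel equals the sum of its two sites, and the USA equals the sum of its three. Rank = 11 - 4 = 7. Without country there are 9 columns and two dependencies, so rank = 9 - 2 = 7. Residual df = 30 - 7 = 23 in both. The fitted space is the same.

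**2. Degrees of freedom for country.** Treatment and baseline have rank 3; adding country gives 4; adding site gives 7. In the listed order, country takes 1 df and site 3. Country has 0 df only when adjusted for site.

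**3. Treatment effect.** Simulated data (30 patients, arbitrary site effects) give the same result with and without country:

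| Site sizes | Difference | SE | p |
|---|---|---|---|
| 6/6/6/6/6 | -3.781695 | 1.421997 | 0.014008 |
| 3/9/3/6/9 | -4.820996 | 1.331345 | 0.001434 |
| 12/6/3/3/6 | -3.540512 | 1.436943 | 0.021645 |

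**4. Arm means.** An adjusted mean is estimable when each country's weight equals the sum of its sites' weights.

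- Countries 1/2 each with sites 1/5 each: Israel has 1/2 against 2/5, so not estimable.
- Nested weights 1/4, 1/4, 1/6, 1/6, 1/6: 1/4 + 1/4 = 1/2, estimable.
- Countries 0.4/0.6 with sites 1/5 each: 1/5 + 1/5 = 0.4, estimable.

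Moving from equal site weights to nested weights raises Israel's share from 0.4 to 0.5, so both arm means shift by 0.1 × the Israel-USA difference. With five sites of 6, the active mean goes from -2.016 to -2.514 and the placebo mean from 1.766 to 1.268. Both shift by -0.498, so the difference between arms does not move.

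**5. Is this peculiar to listing both terms?** No. In a country-only model with five equal sites, equal country weights (0.5/0.5) against observed shares (0.4/0.6) also shift arm means by 0.1 × the country difference.

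**6. Would country alone be better?** Half-widths of the 95% interval in SD units, five sites of 6, 20:10 completers:

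| Assumption | Site | Country only |
|---|---|---|
| No site variance, unstratified (residual SD fixed at 1) | 0.886 | 0.827 |
| No site variance, 4:2 within each site (residual SD fixed at 1) | 0.819 | 0.812 |
| Site explains 25% of variance, unstratified (mean estimated half-width) | 0.757 | 0.779 |

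The third row is on a different scale; its counterpart at zero site variance is 0.877 against 0.819. Site costs about 7% in the first case (0.886/0.827 = 1.07) and under 1% in the second (0.819/0.812 = 1.009). It gains about 3% in the third (0.757/0.779 = 0.97). Break-even is near 16-18% of residual variance.

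**The case for a change.** The strongest case is that this is the only model offered for the efficacy endpoint, in a small study meant to show trends, so adjusted arm means are likely to be printed beside the difference. Three defensible weightings of one simulated data set (sites of 3/9/3/6/9) give active-arm means of -2.775, -3.383 and -1.862. The choice could be made after unblinding, and the supportive multiple-imputation analysis in Section 8.3.2 names no other model. One sentence would settle it.

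What stands is narrow. If adjusted arm means are reported, their weights must be given. That is ordinary reporting detail for any ANCOVA with a geographic factor, and deleting country would not supply it. In the same example the difference is -4.820996 under all three weightings.

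The invariance has limits. If site were random, country would be estimable and the estimate would move slightly (in the example with five sites of 6, -3.769 with country and -3.799 without). If site numbers were reused across countries, the model would be a different one of rank 6 (-3.750 against -3.782). A treatment-by-site or treatment-by-country interaction would also break it. The plan proposes none of these, and unique site coding is a programming matter.

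On precision, the case for country alone needs low site variance and allocation unbalanced within site. Section 5.2 names no stratification factor, but that does not show how the schedule is blocked. Central reading limits reader variation, not differences in scanners or populations between sites. Unlike deleting country, deleting site changes the treatment estimate. Whether to stratify the randomization is a separate question.

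**Conclusion.** No change follows. The wording is redundant by one term, a slip that any analyst or standard software resolves by dropping country or fitting site within country. Both give the same model: rank 7, 23 residual df at 30 completers, and an identical treatment difference, standard error and p-value. The effect on the planned comparison is zero, given fixed, uniquely coded sites and no interaction with treatment.

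The country effect adjusted for site is not estimable, but no country test is planned. Arm-mean weights are missing detail that would be needed under any of the alternatives. Choosing country over site is a trade-off, from about a 7% narrower interval to about a 3% wider one across the assumptions shown, and the documents give neither the site variance nor the within-site balance needed to decide it. Liver fat is a secondary endpoint in an exploratory study, so the point is editorial.
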